6 INTRODUCTION

6.1 Background: Disease

Age-related macular degeneration (AMD) is a common eye condition that has been described as the leading cause of vision loss, affecting 10%–13% of adults over 65 years of age in North America, Europe, Australia, and Asia.¹ AMD is a progressive, degenerative disease affecting the macula, the region of the retina that is most important for visual acuity (VA). It causes damage to the macula, increasingly affecting sharp, central vision over time. While AMD by itself does not lead to complete blindness, the loss of central vision in AMD can interfere with simple everyday activities.² Age is a major risk factor for AMD, with the disease most likely occurring after age 60. Other risk factors include smoking, race, and family history and genetics.

Neovascular AMD is a major cause of loss of central vision in the elderly. While it does not cause complete blindness, it can make daily activities such as driving and reading difficult or impossible. Disease activity in neovascular AMD is lifelong. Even at late stages in the therapeutic course, exudative AMD patients remain at risk for substantial additional visual decline. AMD is a disease of the photoreceptors and the retinal pigment epithelium (RPE). In the aging eye, Bruch's membrane composition changes, RPE function diminishes, and drusen (containing lipofuscin and other toxic waste products of metabolism) is deposited. Vision loss results from the abnormal growth and leakage of blood vessels in the macula.

The main factor influencing AMD progression remains age, with genetics and smoking also having an impact. A meta-analysis of population-based AMD studies reported a global prevalence of 8.7% in people aged 45 to 85 years, with a higher prevalence in Europe and North America than in Asia.³ The authors further predicted that the number of cases worldwide would increase from 170 million in 2014 to 196 million in 2020 and 288 million in 2040.

AMD is divided into “early,” “intermediate,” and “late” types based on severity, with the late type being the most severe.² The late type can be further divided into the dry (atrophic) and the wet (ie, neovascular or exudative) forms. The dry form is less aggressive and accounts for 90% of all AMD cases but only for 10% of cases of blindness due to AMD. Dry AMD may develop into wet AMD. Wet AMD (wAMD) affects 10% of the AMD patients and is the more aggressive form, which, if untreated, leads to rapid severe visual impairment and in many cases, legal blindness.¹ However, 80% to 90% of patients with severe vision loss due to AMD have wAMD.¹

Wet AMD causes rupture of Bruch's membrane, an associated localized inflammatory response, and release of vascular endothelial growth factor (VEGF), which induces choroidal neovascularisation (CNV). The newly formed blood vessels grow through the ruptured membrane underneath the RPE and the retina. These new vessels are fragile and leak blood and proteins and may cause persistent edema below the macula, resulting in permanent damage to photoreceptors and the loss of central vision.

Treatment of wAMD includes photodynamic therapy (PDT) and laser coagulation, (although a recent Cochrane review found that laser coagulation is ineffective at preventing CNV and limiting loss of VA).⁴

To date, standard of care treatment for wAMD is intravitreal (IVT) anti-VEGF therapy, with the VEGF-antagonist pegaptanib (Macugen®; Bausch + Lomb) and the monoclonal antibody ranibizumab (Lucentis®; Genentech/Novartis). Another anti-VEGF treatment for wAMD is afibercept (Eylea®; Regeneron), which is a VEGF-trap that interferes with the biological actions by binding to VEGF-A, preventing it from interacting with its receptors.

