8.3.2 Inclusion Criteria

To be eligible for study entry, subjects must satisfy **all** of the following inclusion criteria:

1. Written and signed informed consent form obtained at Screening before any study-related procedures are performed. Patients must be capable of providing their own consent (an impartial witness must be present in case of illiterate patients).
2. Willingness and ability to undertake all scheduled visits and assessments as judged by the investigator.

3. Newly diagnosed, active subfoveal choroidal neovascularization (CNV) lesion secondary to age-related macular degeneration (AMD) in the study eye. *Note:* active CNV indicates the presence of leakage as evidenced by fluorescein angiography (FA) and intra- or subretinal fluid as evidenced by optical coherence tomography (OCT), which *must be confirmed by the central reading center during Screening:*
 - a. The area of CNV must be $\geq 50\%$ of the total lesion area in the study eye, and
 - b. Total lesion area ≤ 9.0 disc areas (DA) in size (including blood, scars, and neovascularization) as assessed by FA in the study eye
4. BCVA of ≤ 73 and ≥ 49 ETDRS letter score in the study eye using the ETDRS chart (20/40 to 20/100 Snellen equivalent) at Screening.
5. Fellow eye should not be expected to need any anti-VEGF treatment for the duration of study participation based on Investigator's decision.
6. Age ≥ 50 years at Screening.
7. Male and female subjects of childbearing potential must be willing to completely abstain or agree to use an appropriate method of contraception from the time of signing the informed consent form and for the duration of study participation through 3 months after the last dose of study drug. See [Appendix 17.1](#) for examples of acceptable contraception. (The investigator and each subject will determine the appropriate method of contraception for the subject during the participation in the study.)
 - a. A woman of childbearing potential is any woman, regardless of sexual orientation, who meets the following criteria: 1) has not undergone a hysterectomy or bilateral oophorectomy or 2) has not been naturally postmenopausal for at least 12 consecutive months (ie, has had menses at any time in the preceding 12 consecutive months).
 - b. A man of sexual potential is any man who has not been surgically sterilized (eg, has not undergone bilateral orchiectomy).

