8.4.3 Randomization

The receipt and review of the lab report is necessary before randomizing a subject. Upon confirmation of eligibility for a given subject to participate in the study, a unique randomization number for that subject will be assigned via an IWRS. The IWRS will be accessed immediately by study site personnel after confirmation of the subject's eligibility has been recorded. The randomization number for a given subject will be used to identify the study drug that will be administered to that subject.

The randomization scheme will automatically ensure that the study drug assignment for a given subject is random and that an overall 1:1 ratio of assignments to each of the 2 study drug treatments is approximated.

In addition, the randomization scheme will include the following stratification parameters to ensure balanced distribution of assignment to the 2 treatments: eye color (light iris vs dark iris), geographical region where enrolled and the BCVA letters at Baseline (55 or lower, 56 to 65, 66 or higher). Permuted random blocks within each stratification combination will be used to ensure the 1:1 ratio within each combination.

An independent biostatistician will create the randomization scheme, which will remain unavailable to all other masked individuals, until after study completion and subsequent locking of the study database.

Once a randomization number has been assigned, that number must not be used again for any other subject (eg, when a subject is withdrawn from the study, that subject's randomization number must not be used again for any other subject).

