9.1 Pre-treatment

9.1.1 Screening Visit (Visit 1)

- Subjects will provide written informed consent before any study-related procedures may be performed.
- Assess for eligibility (against the inclusion and exclusion criteria).
- Collect full medical history, historical disease data, diagnostic information, and concomitant illnesses/diseases, adverse events (including Baseline events), and concomitant medications.
- Record demographic data, such as ethnic origin, date of birth, and sex.
- Perform a physical examination (PE), including body mass index (height and weight measured). A PE will consist of a routine evaluation of organ systems (including head, ears, eyes, nose, throat, neck, cardiovascular, pulmonary, abdomen, skin, extremities, neurological, lymph nodes, and musculoskeletal).

- At the Screening Visit, the PE will include the collection of the subject's eye color (ie, light iris or dark iris).
- Perform BCVA assessment using the ETDRS at 4 meters, including manifest refraction.
- Perform FA and OCT in both eyes, in which results should be submitted to and confirmed by the central reading center *prior* to Randomization.
- Perform CFP in both eyes.
- Perform SLE of the anterior segment in both eyes.
- Perform dilated fundus examination of the posterior segment in both eyes.
- Measure IOP in both eyes. Goldmann tonometry should be used for pre-injection IOP.
- Record vital signs including blood pressure and heart rate. Systolic and diastolic blood pressure and pulse rate will be measured after patients have been at rest (seated) for at least 5 minutes.
- Collect blood sample for hematology and clinical chemistry tests.
- For females of childbearing potential only, collect urine sample for pregnancy test.
- Record any Baseline events and concomitant medications.

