The secondary estimand of the study for the primary endpoint will use alternate methods of handling data following IEs compared to the primary estimand. This approach will use a treatment policy with respect to IEs such that any data collected following the IE will be used in the analysis. So the scientific question of interest is the between-group difference (Xlucane v Lucentis[®]) in the mean change from baseline in BCVA letter score at Week 8 in patients who fulfil the study eligibility criteria and complete 8 weeks of treatment of study drug, regardless of any other IEs. However, because the study design does not plan for assessments following early treatment discontinuation, a true treatment policy strategy is not possible to apply. As such, any missing data following early treatment discontinuation will be imputed using a hypothetical strategy.

Assumptions for imputing missing data due to IEs and analysis methods for each estimand are detailed in [Section 11.3.7](#).

The change in BCVA letters at Week 8 compared to Baseline using the ETDRS protocol will be analyzed using a mixed model for repeated measures (MMRM). An MMRM approach will be fitted with geographical region of the country where enrolled, visit, eye color (light iris vs dark iris), treatment, and treatment-by-visit interaction as fixed effects, with the baseline BCVA letters and baseline BCVA letters-by-visit interaction as covariates. The treatment differences from the model at Week 8 will be evaluated and a 95% or 90% two-sided CI for the least squares mean difference between groups will be calculated. To prove the 2 products to be biosimilar, the confidence limits for this difference have to be within the equivalence margin of ± 3.5 letters for the primary estimand. The secondary estimand analysis will be supportive of the primary estimand analysis.

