11.3.7 Handling of Missing Data

Any data following an IE, which is deemed to have been impacted by the IE, may be treated as missing data in the analysis in accordance with [Section 11.3.3.1](#).

For the primary analysis of each endpoint/estimand, a missing at random (MAR) approach will be assumed for missing data (ie, the probability of an observation being missing depends only on observed measurements). Sensitivity analyses will be conducted using different missing data assumptions such as missing not at random (MNAR) and missing completely at random (MCAR) within each endpoint/estimand.

For continuous endpoints, a MMRM model will be used (using only evaluable data) to adopt a MAR assumption for the primary analysis. Patients with missing data at a particular time point still contribute to the analysis at that time point based on their other observed data used in the MMRM (ie, visit, treatment, baseline BCVA letter score, geographical region of the country where enrolled, eye color (light iris vs dark iris), and BCVA letter score at other visits) and the known covariance structures between these factors. The sensitivity analyses will use alternate methods (to be detailed in the SAP) of imputing missing data such as multiple imputation with pattern mixture modelling and using evaluable data only. ANCOVA models will be used to analyze such data at the respective visit.

For non-continuous endpoints, alternate methods will be specified in the SAP to impute missing data, although the same mechanisms will be assumed as for continuous endpoints (ie, primary analysis assumes MAR, sensitivity analyses to assess MNAR and MCAR).

Due to the indication under evaluation in this study, it is considered that most missing data due to COVID-19 can be treated as MAR, but this will be evaluated and agreed at the BDRM. Additional subgroup and sensitivity analyses relating to the potential bias from missing data and/or deviations from the protocol during the COVID-19 pandemic will be considered for analysis of all endpoints and added to the SAP prior to database lock.

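### Age, which the protocol calls the main driver of AMD progression and which is already collected, is not in the primary MMRM; pre-specifying it is an optional, low-cost improvement to a valid analysis

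*Combined protocol and SAP*

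**What the plan says.** The disease background in protocol section 6.1 states: "The main factor influencing AMD progression remains age, with genetics and smoking also having an impact". Eligibility in 8.3.2 sets only a lower limit, "Age ≥ 50 years at Screening", so the age range may be wide. The Screening procedures in 9.1.1 include: "Record demographic data, such as ethnic origin, date of birth, and sex". Age is therefore available for every randomized subject.

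Randomization (8.4.3) is stratified by eye color, together with "geographical region where enrolled and the BCVA letters at Baseline (55 or lower, 56 to 65, 66 or higher"; age is not used. The primary MMRM in 11.3.3.1 is "fitted with geographical region of the country where enrolled, visit, eye color (light iris vs dark iris), treatment, and treatment-by-visit interaction as fixed effects". Its one continuous adjustment variable is the acuity score at the start of the study, entered both alone and crossed with visit. Section 11.3.7 lists what informs a missing value: "visit, treatment, baseline BCVA letter score, geographical region of the country where enrolled, eye color (light iris vs dark iris", plus BCVA at other visits. Age appears in neither list.

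Section 11.4 links one baseline variable to the variability of the Week 8 change, and that is baseline BCVA. Technical detail, including the imputation methods, is deferred to a separate SAP whose text is not part of the document reviewed.

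**The concern.** The biosimilarity decision depends on whether one confidence interval, for the difference in mean BCVA change at Week 8, stays inside ±3.5 letters. A baseline variable that predicts the outcome and is left out of the model stays in the residual and widens that interval. The protocol itself singles out age as the leading factor in the disease and already collects it, so its absence from the model needs a reason, and none is given.

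The second strand is missing data. Under the primary estimand, values after early discontinuation, efficacy-relevant non-adherence or fellow-eye anti-VEGF treatment are set aside even when they were collected, and the MMRM then relies on missingness at random given what it contains. Section 11.3.3.1 reports a rise in COVID-19-related deviations. If age is related both to missed or excluded visits and to outcome, a model without age cannot condition on it. That is an inference: the documents give no figure for age and attendance.

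**Working it through.** **Inputs.** SD 10 letters and 580 randomized (11.4); 1:1 allocation, so 290 per arm (8.1); margin ±3.5 letters (8.2.1); two-sided 95% CI for the power statement (11.4). The SD of 10 is taken as the residual SD before age is added, with all 580 contributing at Week 8.

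**Reproducing the plan's figure.**
- SE = 10 × √(2/290) = 0.830 letters. The 95% half-width is 1.96 × 0.830 = 1.628 letters.
- Power at true difference d = Φ((3.5 − d)/SE − 1.96) + Φ((3.5 + d)/SE − 1.96) − 1.
- At d = 0: 3.5/0.830 − 1.96 = 2.25, so power = 2Φ(2.25) − 1 = 97.6%. The exact t version gives 97.5%.
- The same calculation with the 90% CI used for the US decision gives 99.0%.
- If 20% of subjects were non-evaluable (assumed; no dropout rate is stated), 232 per arm remain and power is 92.8%.

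The claim of more than 90% is reproduced without age in the model.

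**Adding age.** Let r be the share of remaining variance that age explains once the planned terms are fitted. The documents do not give r, so it is varied.
- SE with age = 0.830 × √(1 − r).
- Equivalent extra subjects = 580 × (1/(1 − r) − 1).
- 95% range of the shift in the estimate from chance age imbalance = ±1.96 × √r × 0.830.

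Power below is the exact t version. The true difference of 1 letter is an assumption for illustration; the plan does not state one.

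| Assumed r | SE | 95% half-width | Power, d = 0 | Power, d = 1 | Equivalent extra subjects | 95% range of shift |
|---|---|---|---|---|---|---|
| 0 | 0.830 | 1.628 | 97.5% | 85.2% | 0 | 0 |
| 1% | 0.826 | 1.620 | 97.7% | 85.5% | 5.9 | ±0.16 |
| 2% | 0.822 | 1.611 | 97.8% | 85.9% | 11.8 | ±0.23 |
| 5% | 0.809 | 1.586 | 98.2% | 86.9% | 30.5 | ±0.36 |

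**Where chance imbalance sits.** The unadjusted variance of the estimate is 0.8305² = 0.6897. At r = 5% it splits into 0.95 × 0.6897 = 0.6552 (what remains after adjustment) and 0.05 × 0.6897 = 0.0345 (chance age imbalance), which add back to 0.6897. The planned interval already contains the imbalance component. Adjustment removes it from the estimate and from the interval together.

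**The case against.** The strongest objection is that the sentence in 6.1 does not support the step taken from it. It concerns progression of the disease and stands beside prevalence projections. The endpoint is an eight-week change in newly diagnosed eyes, all on monthly ranibizumab. Nothing in the documents says that age predicts that change, least of all once baseline BCVA, region and eye color are in the model. The same sentence also names genetics and smoking. This stands: r could be zero, and then there is no precision gain.

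A reader might infer three stronger things that the documents do not support:
- **That leaving age out biases the comparison.** Under randomization it does not. Imbalance in an unmodelled covariate is random error within the standard error, and the test keeps its error rate. A wider interval also works against an equivalence claim, not for it.
- **That the trial is underpowered without age.** The stated power is met, and still holds with 20% non-evaluable.
- **That a precision gain is guaranteed.** No correlation is documented.

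On missing data, the model already uses baseline BCVA and BCVA at other visits, including Weeks 2 and 4, and 11.3.7 provides for MNAR and MCAR sensitivity analyses and multiple imputation. Age adds something only if it predicts both missingness and outcome beyond these. That too stands; it makes the benefit possible, not shown. The separate SAP may also already include age in some models.

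The objection does not show that adding age would do harm. It shows that the gain is small and may be nil.

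**Conclusion.** The planned primary analysis is valid, its covariate set is a permissible choice, and neither the sample size nor the stated power depends on age. What remains is an optional improvement: a baseline variable that the protocol calls the main factor in progression, and that is already collected, could be added at almost no statistical cost.

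The likely size is small. For an assumed partial R-squared of 1% to 5%, the half-width falls by about 0.01 to 0.04 letters against a margin of 3.5, and power at zero difference rises by 0.1 to 0.6 points (from exact-t values of 97.54% to 97.67% and 98.16%). If age explains nothing, the gain is zero. The support for the missing-at-random assumption is a separate, unquantified benefit, and it rests on the inference that age relates to both missingness and outcome.

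**What to change.** Before interim unmasking, pre-specify age at Screening as a continuous covariate, with an age-by-visit interaction, in the MMRM of 11.3.3.1 (and in the matching synopsis text). Add age to the sensitivity ANCOVA and multiple-imputation models under 11.3.7 and in the SAP, if it is not already there. Keep the model without age as a pre-specified sensitivity analysis, so that the effect of the change is visible.

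Timing matters: once treatment codes are open, a decision to add age would look data-driven.

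The cost is wording in the protocol and SAP, a few model terms and one extra sensitivity run. No new data are needed. Statistically it uses one or a few degrees of freedom out of more than 550, even if age turns out to explain nothing.

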6.2 Xlucane

Xbrane Biopharma AB (referred to as Xbrane) is developing Xlucane as a proposed biosimilar candidate to the EU-licensed Lucentis® (ranibizumab). Lucentis was first approved as a treatment for wAMD in the United States in 2006 and the European Union/European Economic Area (EU/EEA) in 2007.⁵

The active ingredient in Xlucane and Lucentis® is ranibizumab. Ranibizumab belongs to the pharmacological class of VEGF inhibitors and is an antigen binding fragment (Fab) of a recombinant humanized monoclonal antibody (rhuMAb) that binds to the receptor binding site of active forms of VEGF-A, including the biologically active, cleaved form of this molecule, VEGF₁₁₀. VEGF-A has been shown to cause neovascularization and leakage in models of ocular angiogenesis and vascular occlusion and is thought to contribute to pathophysiology of neovascular wAMD. The binding of ranibizumab to VEGF-A prevents the interaction of VEGF-A with its receptors (VEGFR1 and VEGFR2) on the surface of endothelial cells, reducing endothelial cell proliferation, vascular leakage, and new blood vessel formation.⁵

Ranibizumab was originally developed from a murine monoclonal antibody produced using VEGF₁₆₅-immunized mice.⁵ The variable light (VL) and variable heavy (VH) chain from the identified murine monoclonal antibody was fused to human constant light (CL) and human constant heavy (CH1) domains.⁵ The affinity of the new construct for VEGF₁₆₅ was further optimized by phage display.⁶ Crystallographic studies show that the mature Fab fragment binds specifically to VEGF-A and that this interaction occurs at the residues Met81, Gln89, and Gly92 on VEGF-A.^{6,7} It should be noted that these residues are present in the 3 main VEGF-A isoforms in vivo (VEGF₁₂₁, VEGF₁₆₅, and VEGF₁₁₀) and that they are required for binding to the VEGF-A receptors (VEGFR-1 and VEGFR-2).^{6,8}

Prevention of VEGF-A binding to its receptors VEGFR1 and VEGFR2 on the surface of endothelial cells precludes endothelial cell proliferation and neovascularisation, as well as vascular leakage. Ranibizumab contains a light chain with 214 residues and a heavy chain containing 231 residues. In the fully assembled product, the 2 polypeptide chains are linked via a disulfide bond. In addition to the interchain disulfide bond, there

are 2 intrachain disulfide bonds in each polypeptide chain. In a nonreduced environment, the fully assembled product has a molecular weight (MW) of approximately 48 kDa; after reduction, both polypeptide chains can be detected separately (light chain 23 kDa and heavy chain 25 kDa).

